1 PROTOCOL SUMMARY

1.1 SYNOPSIS

Title:	The Effect of an Adaptive Exercise Program on Chronic Inflammation in Spinal Cord Injury.
IRB Number:	A21-006
Study Description:	Long lasting inflammation in the body is related to cardiovascular and respiratory disease, which are the two most common causes of death in people living with spinal cord injury (SCI). Individuals with SCI have been reported to have higher levels of inflammation when compared to healthy individuals. Exercise is a well-known method to reduce inflammation; however, people with SCI are often inactive. The main goal of this study is to determine whether a 12-week adaptive exercise program can reduce inflammation in people with SCI. Participants will be randomized to start exercise immediately or after a 12-week delay.
Specific Aims:	
Specific Aim 1: To examine the effect of a 12-week exercise program on inflammation in individuals with SCI.
 
Specific Aim 2: To examine the effect of a 12-week exercise program on strength and cardiovascular health in individuals with SCI.
 
Specific Aim 3: To observe the impact of a 12-week exercise program on quality of life (QOL) in individuals with SCI.

Endpoints:	
Primary Endpoint: Change in inflammatory biomarkers: CRP, IL-6, TNF-α
 
Secondary Endpoint: Strength: 1-repetition maximum, Cardiovascular: 6-minute submaximal exercise test.
 
Tertiary Endpoint: Spinal Cord Injury-Quality of Life short forms

Study Population:	25 individuals aged 18-70 with a diagnosis of SCI will be recruited for this study.
Description of Sites/Facilities Enrolling Participants:	For in-person visits, participants will attend the exercise program at the HealthPartners Neuroscience Center, located at [name].
Description of Study Intervention/Experimental Manipulation:	The exercise program will be administered by exercise physiologists and physical therapists 3 times per week for a duration of 12 weeks.
Study Duration:	The duration of this study is 2 years.
Participant Duration:	We anticipate that participants will complete all study-related tasks within approximately 6-9 months.

1.2 SCHEMA

1.3 SCHEDULE OF ACTIVITIES

	Pre-screening	Consent	Pre-treatment 1	Pre-treatment 2	Study Intervention	Post-treatment 1	Post-treatment 2	Early Withdrawal Visit
Group 1: Immediate Start	Visit 0	Visit 1	Visit 2	N/A	Visit 3-38	Visit 39	Visit 40	
Group 2: Delayed Start				Visit 3	Visit 4-39	Visit 40	Visit 41	
Review Eligibility	X							
Informed Consent		X						
Randomization		X						
Demographics		X						
Medications		X	X	X	X	X	X	X
Blood Draw- in person			X	X		X	X	X
Strength & Cardiovascular Testing- in person			X	X		X	X	X
SCI-QOL- e-mail survey			X	X		X	X	X
Adverse Events (AE) Reporting					X	X	X	X
Treatment Adherence					X			

VISIT SCHEUDULE DESCRIPTION

All in-person visits will take place at: **HealthPartners Neuroscience Center, [name].**

1. Pre-screening Phone/Video Call (Groups 1 & 2)

- Duration: Approximately 30 minutes
- Research staff will:
 - Provide potential participants information about the study and ask whether they are interested in participating.
 - Determine whether they meet the inclusion/exclusion criteria for the study.
 - Ask participants for permission to communicate through e-mail for the study and assist them in setting up an account if they do not have one (e.g. send them study documents, QOL survey).
 - Schedule Consent Visit if the person is eligible for the study and e-mail the person the Informed Consent, Health Insurance Portability and Accountability Act (HIPAA), and HealthPartners non-discrimination forms.

2. Consent Phone Call (Groups 1 & 2)

- Duration: Approximately 1 hour via phone
- Research staff will:
 - Review the Informed Consent and HIPAA documents with potential participants.
 - Answer any questions of potential participants and ensure they understand the expectations of the study.
 - Ask participants to electronically sign the Informed Consent and HIPAA documents via REDCap and provide them electronic copies for their records.
 - Complete the Demographics short form in the relevant electronic case report forms (eCRFs) in Research Electronic Data Capture (REDCap), a secure web-based system.
 - Randomize the participant and schedule the Pre-treatment visit(s).

3. Pre-treatment Visit 1 (Groups 1 & 2)

- Duration: Approximately 1 hour in person
- Research staff will:
 - Complete the Medication review in REDCap.
 - Have the laboratory staff obtain a blood sample from the patient.
 - Take the patient to the rehabilitation gym for strength and cardiovascular testing (described in detail below)
- Patient will be asked to complete the Spinal Cord Injury-Quality of Life (SCI-QOL) short forms via e-mail survey within 3 days (approximately 30 minutes).

4. Pre-treatment Visit 2 (Group 2 only)

- Duration: Approximately 1 hour in person
- Research staff will:
 - Complete the Medication review in REDCap.
 - Have the laboratory staff obtain a blood sample from the patient.
 - Take the patient to the rehabilitation gym for strength and cardiovascular testing.
- Patient will be asked to complete the SCI-QOL short forms via e-mail survey within 3 days (approximately 30 minutes).

5. Study Intervention (Groups 1 & 2)

- Duration: Each visit approximately 1 hour
- The exercise physiologists will:
 - Complete the Adverse Events (AE) Reporting, Medication Review, and Treatment Adherence in the relevant eCRFs in REDCap.
 - Provide exercise instruction as described in more detail below.

6. Post-treatment Visit 1 (Groups 1 & 2)

- Duration: Approximately 1 hour in person
- Research staff will:
 - Complete the Medication review in REDCap.
 - Have the laboratory staff obtain a blood sample from the patient.

- Take the patient to the rehabilitation gym for strength and cardiovascular testing.
- Patient will be asked to complete the SCI-QOL short forms via e-mail survey within 3 days (approximately 30 minutes).

7. Post-treatment Visit 2 (Groups 1 & 2)

- Duration: Approximately 1 hour in person
- Research staff will:
 - Complete the Medication review in REDCap.
 - Have the laboratory staff obtain a blood sample from the patient.
 - Take the patient to the rehabilitation gym for strength and cardiovascular testing.
- Patient will be asked to complete the SCI-QOL short forms via e-mail survey within 3 days (approximately 30 minutes).

8. Early Withdrawal Visit (For patients who begin the intervention and then withdraw from the study.)

- Duration: Approximately 1 hour in person
- Research staff will:
 - Complete the Medication review in REDCap.
 - Have the laboratory staff obtain a blood sample from the patient.
 - Take the patient to the rehabilitation gym for strength and cardiovascular testing (if medically able).
- Patient will be asked to complete the SCI-QOL short forms via e-mail survey within 3 days (approximately 30 minutes).

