4 STUDY DESIGN

4.1 OVERALL DESIGN

Study Design:

This study is an unblinded, randomized, 2-arm clinical trial.

Hypotheses:

Primary Hypothesis: We hypothesize that exercise will reduce inflammatory biomarkers.

Secondary Hypothesis: We hypothesize that exercise will improve strength and cardiovascular health.

Tertiary Hypothesis: We hypothesize that exercise will improve QOL.

Randomization:

At the consent visit, participants will be randomized into one of two treatment groups. Randomization is explained in **Section 6.3**.

Treatment Groups:

Group 1: 10 participants will begin the exercise program immediately (3x per week for 12 weeks = 36 total).

Group 2: After a 12-week delay, 10 participants will begin the exercise program (3x per week for 12 weeks = 36 total).

Study Intervention:

Exercise sessions will last approximately 1 hour and will be lead by exercise physiologists and therapists. Additional details are discussed in **Section 6.1**.

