Spinal Cord Injury-Quality of Life (Aim 3): Participants will be asked to complete the Spinal Cord Injury-Quality of Life (SCI-QOL) short forms at the pre-treatment and post-treatment visits. The SCI-QOL includes the following domains: basic mobility, fine motor, manual/power wheelchair, self-care, ability to participate in social roles and activities, anxiety, bladder complications, bladder/bowel management difficulties, depression, grief/loss, independence, pain behavior, pain interference, positive affect and well-being, pressure ulcer, resilience, satisfaction with social roles and activities, self-esteem, stigma, and trauma. The SCI-QOL has strong reliability and validity.¹⁵

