9.4.2 ANALYSIS OF THE PRIMARY ENDPOINT(S)

The primary outcome, change in inflammatory biomarker (CRP, IL-6, TNF- α), will be measured using a series of blood draws as described in **Section 6.1**. For our primary analysis, we are interested in the change over the course of the first 3 months, during which group 1 completes the exercise program and group 2 acts as a control. The change in inflammatory biomarker will be calculated by measuring the difference between the first and second measurement for each participant. We will then present the mean change by group with corresponding standard deviations. Analysis of covariance (ANCOVA) will be used to compare the change in each of the 3 inflammatory biomarkers between groups: An unadjusted model will account for a participant's baseline biomarker measurement while an adjusted model will include the set of covariates identified in **Section 9.4.6**. If these analyses identify a significant difference in change of inflammatory biomarkers associated with participation in the exercise program, next steps will assess if this change is still present three months after completing the exercise program. Using data from both groups in aggregate, paired t-tests will be used to compare the inflammatory marker level directly after participation in the exercise program and inflammatory marker levels three months afterward.

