9.4.4 ANALYSIS OF THE TERTIARY ENDPOINT(S)

To evaluate the effect of the exercise program on QOL, SCI-QOL scores will be analyzed similarly to the primary and secondary endpoints. This includes exploration of any observed effects on QOL in the 12-weeks after program completion.

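### The pre-treatment SCI-QOL e-mail survey has a 3-day window but need not precede the first exercise session, so Group 1's baseline and Group 2's control value could be recorded after exercise has begun

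*Combined protocol and SAP*

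**What the plan says.** Section 1.3 sets the timing. At Pre-treatment Visit 2 (Group 2 only) the instruction reads "Patient will be asked to complete the SCI-QOL short forms via e-mail survey within 3 days (approximately 30 minutes". The line for Pre-treatment Visit 1 (both groups) spells out the instrument's name but sets the same window: "short forms via e-mail survey within 3 days (approximately 30 minutes". Blood draw and strength and cardiovascular testing are marked as in-person procedures at the same visits, so the SCI-QOL is the only endpoint not collected on site.

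The visit table in 1.3 numbers the exercise sessions directly after the last pre-treatment visit: Visit 2 then Visits 3-38 in Group 1, and Visit 3 then Visits 4-39 in Group 2. Section 4.1 says of the first group "Group 1: 10 participants will begin the exercise program immediately (3x per week for 12 weeks = 36 total" and of the second "Group 2: After a 12-week delay, 10 participants will begin the exercise program". Section 6.1.2 places the questionnaire more loosely: "short forms at the pre-treatment and post-treatment visits".

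For the analysis, Section 9.4.4 states that "SCI-QOL scores will be analyzed similarly to the primary and secondary endpoints". Section 9.4.2 defines change for the primary endpoint: "The change in inflammatory biomarker will be calculated by measuring the difference between the first and second measurement for each participant". It covers the first 3 months, with Group 2 as the control, and compares groups by ANCOVA; even the model it calls unadjusted includes the baseline value.

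**The concern.** A value labelled pre-treatment should describe the participant before any treatment. For blood and fitness tests the in-person visit secures this. For the SCI-QOL the label rests on when the participant answers an e-mail, and the stated window can run past the first session. A participant who follows the instruction exactly can therefore answer after exercising.

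Two of the four values in the controlled comparison are exposed: Group 1's first measurement (its baseline) and Group 2's second measurement (its control-period outcome). Group 2's baseline is taken 12 weeks before its exercise starts, and Group 1's second measurement follows its programme, so neither is affected.

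The protocol gives grounds for thinking that early sessions could move the answers. Section 2.2.1 lists pain, fatigue and skin breakdown as exercise risks. The SCI-QOL domains in 6.1.2 include pain behaviour, pain interference, pressure ulcer, depression, and positive affect. The scores are self-reported, and participants know their group (4.2, 6.3). At stake is the Aim 3 comparison only; the biomarker, strength and cardiovascular endpoints and the sample size are not touched.

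**Working it through.** The plan gives no figure for SCI-QOL timing, variability or effect, so there is none of its own to reproduce on this point. The power figures in 9.2 concern the biomarkers and do not enter.

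**Step 1: can an on-time survey follow a session?** Inputs from the documents are a 3-day window, 3 sessions per week and 36 sessions. Two assumptions are added: a Monday/Wednesday/Friday or Tuesday/Thursday/Saturday pattern, and session 1 on the first session day after a weekday pre-treatment visit. Session days falling on days 1 to 3 after the visit are then:

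- Mon/Wed/Fri pattern: visit on Monday, day 2; Tuesday, days 1 and 3; Wednesday, day 2; Thursday, day 1; Friday, day 3.
- Tue/Thu/Sat pattern: visit on Monday, days 1 and 3; Tuesday, day 2; Wednesday, days 1 and 3; Thursday, day 2; Friday, day 1.

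Every combination leaves 1 or 2 sessions inside the window (two in 3 of the 10 cases). That is 1/36 = 2.8% to 2/36 = 5.6% of the programme. To follow both sessions, or a single session on day 3, the survey would have to be completed on day 3 after that day's session. If session 1 is more than 3 days after the visit, the count is zero.

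**Step 2: effect on the contrast.** Let b be the ANCOVA slope of the second measurement on the first. Using the change score as the outcome gives the same group difference as using the second measurement, once baseline is in the model. The estimated effect is

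(G1 second − b × G1 first) − (G2 second − b × G2 first).

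Let f be the fraction of surveys in each arm completed after session 1, and s the mean shift in those scores. G1 first rises by fs, which changes the estimate by −b·fs. G2 second rises by fs, which changes it by −fs. Together:

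bias ≈ −(1+b)fs.

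**Step 3: size.** The documents give none of f, s or b, so the following are assumed ranges:

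- f = 0.1, s = 1 point, b = 0.5: 1.5 × 0.1 × 1 = 0.15 points.
- f = 0.3, s = 2 points, b = 0.5: 1.5 × 0.3 × 2 = 0.9 points.
- f = 0.3, s = 2 points, b = 0.8: 1.8 × 0.3 × 2 = 1.08 points, or about 1.1.

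**Step 4: direction.** For a domain where higher is better, a positive s (a lift in mood) makes the estimated benefit too small, and a negative s (soreness, fatigue) makes it too large. If the shifts differ between arms, the bias is −f(b·s1 + s2), where s1 is the shift in Group 1 and s2 in Group 2. With f = 0.3, b = 0.5, s1 = +2 and s2 = −2, this is −0.3 × (1 − 2) = +0.3 points, against 0.9 in size when both shifts are 2 in the same direction.

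**The case against.** The strongest objection is that this argues from silence where text is known to be absent. The schema in 1.2 is not shown, and the amendment history in 10.4 records a widened window for the pre-treatment visit that the readable text does not state. A visit-to-session interval could sit there. The word used for Group 1's start in 4.1 contrasts with a 12-week delay and need not mean the next day. Section 6.1.2 also places physician clearance before exercise and bases prescriptions partly on baseline exercise assessments, which may take some days. All of this stands as a limit: the overlap is permitted by the readable text, not shown to happen.

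Intent is also clear. The visit is named pre-treatment, the table lists the SCI-QOL there and not under the intervention, 6.4 tracks completion of assessments, and 9.4.10 allows a sensitivity analysis that excludes protocol deviations. None of these fixes the order, though. A survey returned on day 2 after a session on day 1 complies with 1.3, so it would not be picked up as a late-survey deviation.

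A reader might infer that the two errors always add and that the bias is 2fs (1.2 points at f = 0.3 and s = 2). The documents do not support that. 2fs is the result for unadjusted change scores, whereas the planned models adjust for baseline, which shrinks Group 1's part to b·fs. The errors add only if early sessions shift scores the same way in both arms, and a common shift across some twenty domains is not established.

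Materiality is low. The endpoint is tertiary, Aim 3 is worded as observing an impact, and with 10 per arm the standard error of an unadjusted difference in means is about √(2/10) = 0.45 SD. That bears on priority; it does not remove the gap.

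**Conclusion.** The concern holds as a gap in the written procedure. The stated window lets a compliant survey follow 1 or 2 of the 36 sessions, provided session 1 falls within 3 days of the pre-treatment visit. Where that happens, Group 1's baseline and Group 2's control-period value no longer describe participants who have not yet exercised.

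The illustrative size is about 0.15 to 1.1 SCI-QOL points. It rests on assumed ranges for f, s and b and on f and s being equal in both arms. The sign is unknown, and the documents give no SCI-QOL standard deviation with which to put it on a standardised scale. It would be wrong to infer that contaminated surveys have occurred or that the SCI-QOL result is invalid. This is a cheap improvement to a tertiary endpoint.

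**What to change.** In Section 1.3, for Pre-treatment Visit 1 (Group 1) and Pre-treatment Visit 2 (Group 2), change the survey window to: within 3 days and before the first exercise session. Staff confirm submission in REDCap before starting that session; a survey still outstanding is completed on arrival.

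In 9.4.4 or 9.4.10, add that any pre-treatment survey time-stamped after session 1 is flagged, that the number per arm is reported, and that the SCI-QOL analysis is repeated without those surveys as a sensitivity analysis. It should not replace the main analysis, because each exclusion removes a participant from an arm of about 10. For participants already enrolled, survey dates, where recorded, can be compared with first-session dates in the same way.

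The cost is one clause and one check. An occasional participant will spend up to 30 minutes on the survey on site before session 1. That slightly changes the mode of completion, from a private e-mail survey to one completed near unblinded staff, so on-site completion should be recorded.

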2 INTRODUCTION

2.1 BACKGROUND & STUDY RATIONALE

Two of the most common causes of death in people living with spinal cord injury (SCI), cardiovascular and respiratory disease, have been linked to chronic low-grade inflammation.¹ Inflammation has also been linked to obesity, pulmonary issues, diabetes, and poor wound healing.² Although some levels of inflammation in the body can be considered “good” (e.g. inflammation occurs during injury repair), chronic inflammation can have negative consequences. Fortunately, chronic inflammation after a SCI could likely be reduced through modifiable risk factors, as described below.

Higher levels of inflammatory biomarkers are observed in SCI when compared to healthy individuals. Biomarkers are measurable substances from the body (e.g. blood serum). C-reactive protein, which is a marker of both inflammation and cardiovascular disease, was reported to be higher in adults with chronic SCI.³ Proinflammatory cytokines (signaling molecules that promote inflammation) interleukin 6 (IL-6) and tumor necrosis factor alpha (TNF- α), and the IL-1 receptor agonist (IL-1RA) (produced in response to infection or inflammation) are also increased.⁴ Finally, Antiganglioside (anti-GM₁) immunoglobulin (IgG), which are antibodies that are typically also present in autoimmune diseases (e.g. Guillain–Barré syndrome), have also been shown to be elevated.⁴ Not only are these inflammatory biomarkers elevated

in individuals with SCI, they are even more elevated in those with medical complications (e.g. urinary tract infection, pressure ulcers).⁴

A well-known method to reduce inflammation is through exercise; however, due to limitations in mobility, individuals with SCI are among the most sedentary and inactive in the world.⁵ Muscle atrophy, damaged muscle innervation, and reduced muscle activation create barriers for individuals with SCI to exercise. In addition, exercise conditioning in persons with SCI is complicated, because its benefits can be potentially counterbalanced by both ineffective exercise activities and the consequences of imprudent exercise, lending to further injury and accelerated musculoskeletal decline. Individuals with SCI also frequently encounter challenges and barriers when navigating a typical gym space. Therefore, individuals with SCI may be limited in their ability to achieve anti-inflammatory benefits through exercise.

While exercise has been shown to reduce biomarkers of inflammation^{6,7} and increase the release of anti-inflammatory proteins⁷ in healthy individuals, it has not been extensively examined in individuals with SCI. In one study, CRP, IL-6, and TNF- α were all reduced in individuals with SCI after participation in a 10 week cycling exercise program.⁸ In another study, CRP and erythrocyte sedimentation rate (ESR; test to detect inflammation) were both reduced in individuals with SCI following a 6-week body weight supported treadmill training program.⁹ However, these studies included small sample sizes (18 and 14, respectively), did not include a control group, examined biomarkers immediately after the program, and included only cardiovascular exercise. In another study that included both individuals with SCI and multiple sclerosis (MS), there was a significant decrease in TNF- α after one exercise session.¹⁰ However, these results included both patients with SCI and MS and only a single exercise session. Thus, the generalization of the results, the long-term effects, and the effects of strength training are not yet known.

While there is limited evidence that an exercise program can reduce inflammation in individuals with SCI, exercise has been shown to have other important beneficial effects. A recent review found evidence that exercise can improve fitness (cardiorespiratory fitness, power output, muscle strength) and cardiometabolic health (body composition, cardiovascular risk) of individuals with SCI.¹¹ Another review reported evidence that exercise can greatly improve the physical and psychosocial well-being of individuals with SCI.¹² As the result, if the barriers to exercise participation after a SCI can be overcome, individuals may have multiple positive health benefits. For this study, we anticipate that a 12-week adaptive exercise program will reduce chronic inflammation and improve overall health in individuals with SCI.

2.2 RISK/BENEFIT ASSESSMENT

2.2.1 KNOWN POTENTIAL RISKS

Exercise

Potential risks of exercise in individuals with SCI include autonomic dysreflexia, musculoskeletal injury, hypotension, thermal dysregulation,¹³ pain, fatigue, and skin breakdown. The exercise program will be supervised by exercise physiologists to reduce these risks.

Blood Draw

Potential risks of blood draws include pain, bruising, dizziness, and local infection.

Assessments/Questionnaires (SCI-QOL)

The Spinal Cord Injury-Quality of Life short forms are standardized questionnaires that will measure personal perception of life. The questions on these assessments may make participants feel uncomfortable because some parts may be easy to answer, while some parts may be difficult or tiring. Filling out the questionnaires may also cause individuals to feel uncomfortable or upset.

Loss of Confidentiality

There may be a slight possibility of breach of confidential information that was collected. However, the following procedures will be implemented to reduce this risk:

- Data collection and reporting tools will be developed and stored internally.
- Data collected and stored electronically will remain confidential and secure (e.g. secured server and password protected files [REDCap]).
- Study binders will be stored in a locked file cabinet within a locked office.
- After the study is closed, all subject identifiers and blood samples will be destroyed.

